6.1. Statistical Plan

6.1.1. Sample Size Determination

Sample size is based on a possible reduction in risk of neonatal mortality/BDP in infants at 36 weeks PMA receiving the SI intervention compared to those who receive the standard PEEP/CPAP. The significance level was set at $\alpha=0.038$ (due to the interim analyses), and power at 80%. Based on information from the recent multi-center NICHD SUPPORT trial² and the COIN trial,²⁰ we estimate that the baseline rate of neonatal mortality/BDP in the standard or care (control) arm by 36 weeks is 65%.

In order to detect an absolute risk reduction of 12.5%, 263 subjects per treatment arm are required. We anticipate virtually no loss to follow-up for the primary endpoint as infants will likely still be hospitalized because of their condition, will be under constant and continuing medical care. We have inflated the estimate by 1.12 to allow for twins and multiples to be randomized together. With this inflation in mind, the target sample size for this study is 300 subjects per arm.

For the secondary outcomes available in all subjects, with 263 subjects per arm (ignoring the twin correction factor), there will be 80% power to detect a difference of 0.24 standard deviation units in continuous outcomes, and a hazard ratio of 0.77 in survival outcomes under a proportional hazards assumption. Some secondary outcomes will not be available due to death of the infant, or loss to follow-up after discharge from the NICU. Overestimating these rates at 50%, we assume 130 subjects per arm will be available for the longer term secondary outcomes. With this sample size we will still have sufficient power to detect a clinically meaningful difference of at least 17% in event rates (or odds ratio of at least 2.0).

6.1.2. Methods of Analysis

The proposed study is a two-arm parallel design of two alternative courses of treatment. A conventional “as-randomized” analysis (or “intention-to-treat” analysis) will estimate whether the

experimental therapy is superior to conventional therapy in avoiding treatment failure, and is at least as good as conventional therapy in avoiding adverse events.

SAS will be used for secondary data management and descriptive statistics. SAS datasets will be downloaded at least weekly from the study database for analysis. Graphics will be prepared using Stata v11 (or later) (Stata Corp, San Antonio TX, 2009) and the R programming package (The R Foundation for Statistical Computing, Vienna, Austria, 2011). Analyses will be implemented in SAS.

6.1.2.1. Descriptive Statistics

Although randomization at baseline should balance observed and unobserved differences between the treatment arms by measured and unmeasured confounders, extra precautions are needed to guard against the potential bias of baseline covariates with chance imbalance from finite sample sizes. Initial analysis will describe the distribution of data. We will characterize both treatment arms by demographic variables and all covariates of interest. Means, standard deviations, medians, and ranges will be computed for measured continuous variables; marginal distributions will be used for categorical factors. Graphical methods including histograms, scatterplots, and boxplots, will be used in order to understand aspects of data quality and examine assumptions (such as normality) underlying statistical models.

6.1.2.2. Analysis of Primary Outcome

The primary endpoint to be used for efficacy evaluation is the rate of Death or BPD at 36 weeks gestation age. The primary hypothesis to be tested is that the treatment therapy results in a decreased event rate. Although a proportion's test is used for sample size calculations, rates will be compared using logistic regression, which will allow for control of covariates, as well as investigation of effect modification. Potential covariates include gender, gestational age, initial heart rate, maternal corticosteroids use, and small for gestational age (SGA). Clinical site will be used as a stratifying factor to control for any confounding by site through residual, site-level treatment imbalance. The logistic regression will be estimated using a generalized estimating equation (GEE) in order to adjust for the inherent correlation expected with multiples. Standard regression diagnostics will be used to assess model adequacy, and to examine for potential outlying or influential data points.

Prior studies offer no basis for assuming a priori interactions between treatment arms and subgroups defined by sex, race/ethnicity, gestational age, site or a combination of these groups, beyond that already controlled for in the randomization. For that reason, preplanned tests for interactions with treatment assignment are not warranted, and not powered for. We propose, however, to table all results by subgroups for descriptive purposes and to explore in secondary analyses possible subgroup differences by treatment group, solely for purposes of generating hypotheses for future studies. In particular, there is interest in exploring subgroups defined by:

- Consenting procedure which may vary by site (antenatal vs. deferred consent). While consenting procedure differences may result in some selection bias, this will be implicitly adjusted for with

the already planned clinical site stratification factor. Additionally, the sample size still results in 80% power at $\alpha=0.038$ for the primary outcome even if the selection bias results in a reduced control arm rate.

- Route of treatment (facemask vs. nasopharyngeal tube). While not expected to modify the intervention effectiveness, exploring this difference will be important for future study design and clinical practice.
- Enrollment date. Clinical practices unrelated to this intervention, as well as increased intervention experience, could result in changes in the clinical effectiveness of the intervention over time (positively or negatively). We will explore graphically any temporal trends in the intervention effect, and will allow/test for a time-varying treatment effect via a functional logistic regression model, if needed (for which the original power calculations are conservative).²¹

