5. FINAL DATA ANALYSIS UPON COMPLETION OF TRIAL

Upon completion of the primary outcome at 36 weeks PMA, after all data has been entered in the database and query resolution is complete, the primary statistical analysis and description of the data will be performed. The final analysis for the 22-26 month cGA secondary outcomes will be completed separately, after that data has been entered in the database and cleaned. The staff biostatistician under the direction of the faculty biostatisticians will produce a final report outlining all analyses and interpretation of the results. This report will be used as the basis of the primary manuscript to be prepared for publication. Details of the analyses and statistical methods to be included in the final report are outlined below. All statistical tests described below will be conducted using a two-sided level of significance.

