5.4.3 Group Sequential Boundary for Primary Endpoint

To avoid inflating the overall Type I error rate for the primary analysis of efficacy, an O'Brien-Fleming boundary will be used to calculate the nominal significance level to which the interim p-value for the primary endpoint is compared. The efficacy boundary is 0.038 at the final analysis.

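### Calling the sample-size calculation conservative for a time-varying treatment effect is unsupported and not true in general

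*Protocol*

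**What the plan says.** Protocol 6.1.1 sizes the trial for a single effect on death or BPD, from a control rate of 65%, at alpha 0.038 and 80% power: "In order to detect an absolute risk reduction of 12.5%, 263 subjects per treatment arm are required". An allowance of 1.12 for multiples leads to the target of 300 per arm. Protocol 6.1.2.2 confirms which test lies behind the figure: "Although a proportion's test is used for sample size calculations, rates will be compared using logistic regression". The SAP fixes the final level in 5.4.3 ("The efficacy boundary is 0.038 at the final analysis") and makes the final tests two-sided in section 5.

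Protocol 6.1.2.2 also says that "preplanned tests for interactions with treatment assignment are not warranted, and not powered for". It then lists subgroups of interest for hypothesis generation. The last is enrollment date, because practice and experience with the maneuver may change the effect in either direction. The plan is to look at trends graphically and, if needed, to allow or test for a time-varying effect by functional logistic regression, "for which the original power calculations are conservative". SAP 5.4.1 repeats both statements. Neither document gives a size or shape for the trend, the model's degrees of freedom, or a power figure for this analysis.

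**The concern.** The sample-size calculation contains no time term. A treatment effect that varies with enrollment date is a treatment-by-time interaction, and interactions usually need several times the sample of the main effect. A model that merely allows for variation spends extra degrees of freedom, which costs power when there is little variation to find. Neither consideration fits the word conservative.

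What is at stake is interpretation. The plan itself names growing experience and changing practice as reasons for drift. A reader told that power for this question is conservative could give a flat trend more weight than it can bear.

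**Working it through.** **Inputs.** Control rate 0.65, planned reduction 0.125 (so 0.525 with SI), power 0.80, 263 and 300 per arm (protocol 6.1.1); alpha 0.038 two-sided (protocol 6.1.1; SAP 5 and 5.4.3). The normal quantiles are 2.0749 (for 0.981) and 0.8416 (for 0.80). Assumptions, because the documents give none: the effect steps once between two equal halves of enrollment, the control rate stays at 0.65, and infants are independent.

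**1. The plan's own figure.** With mean rate 0.5875, the pooled two-proportion formula is

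n = [2.0749 × √(2 × 0.5875 × 0.4125) + 0.8416 × √(0.65 × 0.35 + 0.525 × 0.475)]² / 0.125² = 262.6, so 263 per arm.

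This matches exactly, so the calculation being called conservative is identified: one constant effect, 1 degree of freedom.

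**2. Testing whether the effect changes.** Let the reduction be d1 in the first half and d2 in the second, averaging 12.5 points. With n per arm, each half has n/2 per arm, and

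SE = √{[2 × 0.65 × 0.35 + p1(1 − p1) + p2(1 − p2)] / (n/2)}, where p1 = 0.65 − d1 and p2 = 0.65 − d2;

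power ≈ Φ(|d2 − d1| / SE − 2.0749).

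For 6.25 then 18.75 points (a 12.5-point change), the bracket is 0.9459. With n = 263, SE = √(0.9459/131.5) = 0.0848, the ratio is 0.125/0.0848 = 1.474, and power is Φ(−0.601) = 0.27. With n = 300, SE = 0.0794 and power is 0.31.

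| Reduction, early then late | Change | Power, 263 per arm | Power, 300 per arm |
|---|---|---|---|
| 10 then 15 points | 5 | 0.07 | 0.07 |
| 6.25 then 18.75 points | 12.5 | 0.27 | 0.31 |
| 0 then 25 points | 25 | 0.82 | 0.87 |

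At alpha 0.05 the middle row becomes 0.31 and 0.35. For 80% power at alpha 0.038, a 12.5-point change needs 2 × 0.9459 × (2.0749 + 0.8416)² / 0.125² = about 1,030 per arm, 3.9 times 263. The smallest change detectable with 80% power is about 24.5 points at 263 per arm (23 at 300), roughly twice the planned effect.

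Shape matters. In a simulation of logistic regression with a linear treatment-by-time term (263 per arm, 1,500 runs, Monte Carlo error about 1 point), a reduction rising steadily from 6.25 to 18.75 points gave the interaction test power of 0.11; a rise from 0 to 25 points gave 0.34.

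**3. Testing treatment while allowing the effect to vary.** Under a constant 12.5-point effect the noncentrality is (2.0749 + 0.8416)² = 8.51. Noncentral chi-square power at alpha 0.038 is 0.80 on 1 df, 0.71 on 2 df, 0.64 on 3 df and 0.59 on 4 df.

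If the effect does vary, a joint 2-df test by halves has noncentrality equal to the sum over halves of d² × (n/2) / [0.65 × 0.35 + p(1 − p)]. At 263 per arm:

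- 10 then 15 points: 2.77 + 6.20 = 8.96, power 0.73
- 6.25 then 18.75 points: 1.09 + 9.71 = 10.80, power 0.82
- 0 then 25 points: 0 + 17.58 = 17.58, power 0.96

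In the linear-trend simulation the joint 2-df test had power 0.74 for 6.25 rising to 18.75 points, and 0.82 for 0 rising to 25 points, where the constant-effect test had 0.78.

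**The case against.** The strongest defense is that the plan speaks of allowing for a time-varying effect as well as testing for one. On the allowing reading, conservative would mean that the flexible comparison gains power when the effect really does vary. That can happen: under a 6.25-then-18.75 step the joint test reaches 0.82 against 0.80, and under a strong trend it gains more. A reader might therefore infer from the figures above that the statement is always false; it is not. What remains is that the gain depends on the size and shape of the trend, and the documents set no such condition. A methods paper is cited beside the statement, but neither document reports a calculation from it.

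A reader might also infer a flat contradiction within 6.1.2.2. The sentence saying that interactions are not powered for follows from a list of sex, race/ethnicity, gestational age and site, which omits enrollment date. Its wording is general and enrollment date is listed beneath it, so the two statements sit uneasily together, but they do not collide head-on.

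Finally, the functional model is used only if needed, and these subgroup analyses are already described as hypothesis-generating. That stands. Nothing suggests that the model replaces the primary test, so the 71% and 64% figures are not a loss of power in the primary comparison.

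**Conclusion.** The statement is unsupported in both documents and untrue in general. As a test for change over enrollment, the design has about 27% to 31% power at alpha 0.038 for a 12.5-point step between halves, and less for a linear change of the same total size. As a joint test under a constant effect, it has about 71% (2 df) or 64% (3 df) power against 80%. Only for a joint test under a sufficiently strong trend can the word hold.

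These figures rest on assumed trend shapes and ignore clustering of multiples. The 300-per-arm values are therefore optimistic, since the protocol adds the infants beyond 263 to allow for multiples.

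The documents do not support reading this as a fault in the primary analysis: the 263 reproduces exactly, and the sample size, alpha and stopping boundaries are untouched. It is a minor correction to one phrase about an optional exploratory analysis.

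**What to change.** Delete the parenthesis in the enrollment-date item of protocol 6.1.2.2 and of SAP 5.4.1. If the authors prefer to keep a statement about power, replace it with the assumed trend shape and size, the model's degrees of freedom, the alpha and the resulting power. A single figure such as one-third should not be inserted without those assumptions, because it describes a step between halves and not a linear trend.

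In either case, add that the treatment-by-time estimate will be reported with its confidence interval, so that a flat trend is not taken as well-powered evidence of no drift. The cost is one phrase in each document and one line of reporting; design, data collection and conduct do not change.

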6.1.3. Analysis of Secondary Outcomes

Secondary outcomes will be analyzed using similar procedures to the primary outcome. Comparisons between treatment arms will use logistic regression (dichotomous outcomes), linear regression (continuous outcomes), or survival analysis (survival time outcomes), as appropriate.

6.2. Interim Analysis

Since neonatal safety is a consideration in this study, we have chosen to use a group sequential design. Thus, in addition to the final analysis, we are planning on performing two interim statistical analyses during the course of this study. The purpose of the interim analyses will be to determine whether or not there is sufficient evidence of a difference between the treatment arms in the primary endpoint such that the trial should be discontinued prior to reaching the target accrual goal. The interim analyses will be performed after approximately 1/3 (200 subjects) and 2/3 (400 subjects) of the total required patients have completed their primary outcome. An additional safety review will be undertaken after 1/6 (100 subjects) have completed their primary outcome.

The primary outcome for the interim analyses will be the comparison of death/BPD between the treatment arms. This comparison will be accomplished by means of a simple generalized estimating equation (GEE) model for death/BPD versus treatment (since adjustment for multiples will be needed). An approximate O'Brien-Fleming boundary will be used at each interim look to calculate the nominal significance level to which interim p-values are compared.²² Using the O'Brien Fleming spending function, the three analyses (2 interim + final) should use the following incremental α values (0.0002, 0.012, and 0.038) in order to achieve an overall $\alpha=0.05$.

Stopping criteria are for:

(1) Clear superiority. Whether the experimental treatment is clearly inferior to standard therapy. For these calculations, we trade off the power to detect a difference and the size of that difference. Assuming $\alpha=0.0002$ for boundaries for the initial interim analysis when 200 children have been followed to completion, power is limited except to detect large reductions in outcomes of death and BPD. For example, power is approximately 0.81 to detect a reduction from 65% in the conventional therapy to

32.5% in the experimental therapy, a 50% relative reduction. For the second interim analysis, using $\alpha=0.012$, power with 400 children followed is about 0.85 to detect an absolute reduction from 65% to 40% in the risk of death plus BPD. Thus, early or premature stopping for superiority is unlikely, without dramatic improvement from experimental treatment.

(2) Inferiority. Power is limited to identify inferiority of the experimental treatment, with 0.8 power to demonstrate a 15% point increase in the risk of outcome from 65% in the standard therapy to 80% in the intervention.

(3) Futility. Early stopping based on futility of the primary outcome will not be considered independently of the secondary clinical and safety outcomes. In the event that the intervention arm has equivalent BPD/death rates to the standard care arm, it would still be clinically useful to know if the intervention improves any of the secondary outcomes (that are closer to the time of the intervention) or decreases the serious adverse event rate.

(4) Safety.

(a) Early stopping based on inferior safety and non-inferior efficacy must be based largely on descriptive data and close examination of adverse events. With 200 subjects per group at a second early stopping review, and assuming that the experimental therapy is actually no worse than conventional care, observed risk in the experimental group would have to be at most 0.5 (risk of death and BPD) to have 80% power to show non-inferior efficacy (with $\alpha = 0.012$).

(b) To justify stopping for non-inferior efficacy and superior safety again will require a substantial observed improvement in the experimental arm at the second early stopping time.

(c) Another safety outcome is the rate of pneumothorax, pulmonary interstitial emphysema (PIE), and/or other serious adverse events (that have been adjudicated as potentially relating to the intervention; see section 8.2.2). In order to minimize the risk, this safety outcome will be compared between treatment arms after 1/6 (100 subjects) have completed the primary outcome, as well as at the two planned interim analyses for the primary outcome (1/3 and 2/3), since we would not expect any statistically significant differences in the rate after 100 subjects (with O'Brien-Fleming $\alpha 0.000002$). Instead, we will look for a clinically meaningful double the risk in the intervention versus standard care arms.

In summary, given the projected number of patients to be enrolled, early stopping will be unlikely unless the observed effect of experimental care is clearly better or worse than standard care at the planned early stopping assessment times.

The results of the interim analyses will be judged by the DSMC. This committee will act completely independently of the clinical investigators, including the Principal Investigators. However, the ultimate decision to stop the study will rest with the steering committee.

Note: An adaptive design was not used for this study. The efficacy improvement was minor over the conventional design.

7. Trial Management

Project and data management support will be provided by the research team at the Clinical Research Computing Unit (CRCU), and the staff statistician at Biostatistics Analysis Center (BAC). Both of these groups are under the direction of Drs. [name] (co-PI), and [name]. Initial stages of data management will be done by experienced clinical data managers (CDMs), database developers, , supported by computer system analysts, programmers, and information technology (IT) specialists. These persons will be responsible for data quality and timeliness, documentation of processes and procedures, and training of data management staff.

Every effort will be made to monitor data collection and entry and to correct errors, inconsistencies, ambiguities, and omissions in real time. Data will be entered directly into a secure, backed-up, 24-hour, web-based database using electronic case report forms (CRFs) developed by CRCU staff with the assistance of project investigators and statisticians. Data entry screens will incorporate range and logical edit checks, both within and across forms. Data entry will be followed daily with manual and programmed checks and edits for errors and omissions. A data monitoring plan written before the start of data collection will serve as a reference guide for the development of case report forms (paper and electronic versions), data handling conventions, reporting, data dictionaries, supporting meta data, as well as project closeout activities, communication and coordination plans among the PIs, clinical teams, sites coordinators, and staff and faculty-level statisticians.

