2.3 Study Endpoints

The primary endpoint for this study is both an efficacy and safety endpoint. Improved death / BPD rates suggest efficacy, while worse rates suggest a safety problem. As such, all comparisons are inherently two-sided. Interim and final analyses present the classic spectrum of decisions: superiority, non-inferiority, and inferiority.

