4. INTERIM ANALYSIS

Since neonatal safety is a consideration in this study, we have chosen to use a group sequential design. Thus, in addition to the final analysis, there will be two interim statistical analyses during the course of this study. The purpose of the interim analyses will be to determine whether or not there is sufficient evidence of a difference between the treatment arms in the primary endpoint such that the trial should be discontinued prior to reaching the target accrual goal.

Interim analyses will be performed after approximately 1/3 (200 subjects) and 2/3 (400 subjects) of the total required patients have completed their primary outcome. An additional safety review will be undertaken after 1/6 (100 subjects) have completed their primary outcome. The results of the interim analyses will be presented to the SAIL Data Safety and Monitoring Committee (DSMC). The primary outcome for the interim analyses will be the comparison of death/BPD between the treatment arms. This comparison will be accomplished by means of a simple generalized estimating equation (GEE) model for death/BPD versus treatment (since adjustment for deliveries with multiple babies will be needed). An approximate O'Brien-Fleming boundary will be used at each interim look to calculate the nominal significance level to which interim p-values are compared (O'Brien PC, 1979). Using the O'Brien Fleming spending function, the three analyses (2 interim + final) should use the following incremental α values (0.0002, 0.012, and 0.038) in order to achieve an overall α =0.05.

There are four comparisons to warrant early stopping: (1) Clear superiority: Superiority of the intervention is sufficiently large that the study should be discontinued because equipoise is lost and randomization should no longer proceed. (2) Futility: The evidence in favor of the intervention is such that at the completion of the study, there is inadequate power to detect an improvement and the study should be dropped. (3) Inferiority: The evidence shows that the intervention is worse than the control and the study needs to be stopped. (4) Safety: Secondary safety outcomes that are considered serious adverse events possible related to the study are clinically higher in the intervention group. (See also section 4.4 for additional safety outcomes).

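### Second-interim power for 65% vs 40% is about 0.99, not 0.85, and crossing for superiority by that look is not unlikely at the planned 12.5-point effect

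*Protocol*

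**What the plan says.** Protocol 6.2, item (1) on clear superiority, and the matching item in SAP 4 give one power example for each interim look.

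- **First look** (200 children, alpha 0.0002): power of roughly 0.81 for 65% vs 32.5%.
- **Second look** (400 children, alpha 0.012), in the plan's words: "power with 400 children followed is about 0.85 to detect an absolute reduction from 65% to 40% in the risk of death plus BPD".

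Both documents then infer that "early or premature stopping for superiority is unlikely, without dramatic improvement from experimental treatment".

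The design effect is much smaller than either example. Protocol 6.1.1 takes a control rate of 65% and states: "In order to detect an absolute risk reduction of 12.5%, 263 subjects per treatment arm are required".

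The opening words of the same item, in both documents, describe the clear-superiority criterion as the experimental treatment being inferior to standard therapy. The list of stopping comparisons earlier in SAP 4 defines it the other way: "Superiority of the intervention is sufficiently large that the study should be discontinued because equipoise is lost".

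**The concern.** A 25-point difference tested on 400 infants is a very large signal, and 0.85 looked too low for it. The trial claims 80% power for half that difference with 263 per arm at alpha 0.038.

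The figure matters because of the inference drawn from it. This item is the documents' only account of how the superiority boundary behaves at the second look. The DSMC judges the interim results, and in the protocol's words "the ultimate decision to stop the study will rest with the steering committee". Both bodies would read the item as saying that a superiority crossing at 400 infants is to be expected only with an effect well beyond the planned one. If crossing is in fact common at the planned effect, a result of 12 to 13 points at that look could be taken as surprising or premature when it is what the design predicts.

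**Working it through.** **Inputs**

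- Rates 65% and 40%, 400 children, alpha 0.012: Protocol 6.2 (1) and SAP 4 (1).
- 200 per arm: "With 200 subjects per group at a second early stopping review" (Protocol 6.2, safety item), consistent with the 1:1 allocation in Protocol 4.4.4.
- Two-sided test: "As such, all comparisons are inherently two-sided" (SAP 2.3).
- Planned effect 65% vs 52.5%, inflation of 1.12 for multiples, virtually no loss to follow-up: Protocol 6.1.1.

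**Formula** (normal approximation, pooled variance under the null, n per arm):

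power = Φ( [ |p1 − p2| − z·√(2·p̄(1−p̄)/n) ] / √( [p1(1−p1) + p2(1−p2)]/n ) ), where p̄ = (p1 + p2)/2 and z is the two-sided critical value.

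**Step 1: the plan's other figures, same formula**

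| Comparison | n per arm | alpha | Stated | Computed |
|---|---|---|---|---|
| 65% vs 52.5% (6.1.1) | 263 | 0.038 | 0.80 | 0.801 |
| 65% vs 32.5%, first look | 100 | 0.0002 | about 0.81 | 0.824 |
| 65% vs 80%, inferiority | 200 | 0.012 | 0.8 | 0.805 |

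The inferiority sentence gives no n or alpha; the second-look values are assumed here. All three agree with the plan to within 2 percentage points.

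**Step 2: the disputed figure**

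65% vs 40%, n = 200, alpha 0.012, z = 2.512, p̄ = 0.525:

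- null SE = √(2 × 0.525 × 0.475 / 200) = 0.0499
- alternative SE = √((0.2275 + 0.24)/200) = 0.0483
- (0.25 − 2.512 × 0.0499)/0.0483 = 2.58, so power = **0.995**

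With 1.12 as a design effect, n = 200/1.12 = 178.6 and power = **0.989**.

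Other two-sided forms at 200 per arm give 0.996 (unpooled), 0.993 (logistic Wald), 0.995 (arcsine), 0.993 (continuity-corrected) and 0.993 (Fisher exact). At 178.6 per arm, the forms other than Fisher, which was not run there, give 0.985 to 0.991. No form comes near 0.85.

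**Step 3: where 0.85 would be right**

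- At 200 per arm: 65% vs 47.5%, a 17.5-point difference. At 178.6 per arm: 65% vs 46.4%, or 18.6 points.
- For 65% vs 40%, power is 0.856 with 100 per arm. The stated value may therefore come from using 200 children in total; this is an inference and nothing in the documents says so.
- Clustering would need a design effect of about 2.03 to bring power down to 0.85, against the 1.12 allowed.

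**Step 4: the conclusion drawn from it**

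For 65% vs 52.5%, p̄ = 0.5875 and n = 200, the null SE is 0.0492. The second-look boundary is then crossed at an observed difference of 2.512 × 0.0492 = 0.124, about 12.4 points (13.1 with the 1.12 factor). That is essentially the planned effect.

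| True 65% vs 52.5% | No factor | 1.12 as design effect |
|---|---|---|
| Crossing at look 1 | 0.026 | 0.021 |
| Crossing by look 2, joint normal (correlation √½) | 0.511 | 0.455 |
| Crossing by look 2, simulation | 0.52 | 0.45–0.46 |
| Power over all three looks | 0.856 | 0.813 |

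So 0.511/0.856 = 60% (0.455/0.813 = 56% with the factor) of the trials that end significant at the planned effect would have crossed by the second look.

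**The case against.** The power error itself is hard to dispute. The case against going further has four parts.

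1. **The word dramatic is undefined.** Crossing needs an observed difference of 12.4 to 13.1 points. The protocol's background says that BPD has improved little despite much research, so 12.5 points could fairly be called dramatic. For smaller true effects the sentence holds: crossing by look 2 has probability 0.06 to 0.07 at 65% vs 60% and 0.17 to 0.19 at 65% vs 57%. It also holds at look 1 for the planned effect.
2. **Crossing is not stopping.** The sentence concerns stopping, which is a committee decision.
3. **Power of 0.85 at 25 points is not a claim that 25 points is needed to cross.** The text never says that it is.
4. **No decision rule uses the figure.** Interim p-values are compared with fixed nominal levels.

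The second and fourth points stand and limit how serious this is. The third is literally correct; what can be said is that the item gives the reader no other guide to the second look. The first does not rescue the sentence. The inference is drawn directly from examples of 32.5 and 25 points, and at the second look it survives only if the trial's own design assumption counts as dramatic.

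**Conclusion.** The concern holds. The stated second-look power of 0.85 is wrong in both documents: it is 0.995, or 0.989 with the multiples factor. The error is isolated, since the neighbouring figures reproduce.

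The inference that early stopping for superiority is unlikely is sound for the first look but fails for the second at the planned effect, where crossing by then is close to an even chance: 0.51 to 0.52 ignoring multiples, about 0.46 allowing for them. The description of clear superiority as inferiority is a separate wording slip that contradicts SAP 4's own definition.

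These results assume a 65% control rate, equal arms, 0.012 used as the nominal second-look level (as the documents use it in their power statement), and, where stated, 1.12 applied as a design effect at the interim looks. The consequence is a misleading expectation for the DSMC and steering committee. The test, boundaries, alpha and sample size are untouched.

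**What to change.** Make the same three edits in Protocol 6.2 (1) and SAP 4 (1).

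1. Give the second-look power as about 0.99 for 65% vs 40%, and add that 0.85 corresponds to 65% vs about 47%.
2. Replace the sentence on early stopping being unlikely with a statement along these lines: if the true effect is the planned 12.5 points, the chance of crossing the superiority boundary is about 2 to 3% at the first look and about 45 to 52% by the second. The lower end of each range treats the 1.12 factor as a design effect and the upper end ignores multiples. The decision to stop remains with the DSMC and steering committee as already described.
3. Change the description of clear superiority so that it refers to the experimental treatment being superior, in line with the definition earlier in SAP 4.

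The closing summary sentence of the stopping section can stay. The cost is one figure, one sentence and one word in each document, with no change to boundaries, alpha, sample size or conduct.
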